3.2 Exclusion Criteria

3.2.1 History of another malignancy.

Exception: Patients who have been disease-free for 3 years, or patients with a history of completely resected non-melanoma skin cancer or any carcinoma in situ and/or patients with indolent second malignancies, are eligible. Consult the CTEP Medical Monitor if unsure whether second malignancies meet the requirements specified above.

- 3.2.2 History of interstitial lung disease or pneumonitis.
- 3.2.3 Any major surgery, extensive radiotherapy (>15 days of treatment), chemotherapy with delayed toxicity, biologic therapy, or immunotherapy within 21 days prior to first dose of study treatment and/or daily or weekly chemotherapy without the potential for delayed toxicity within 14 days prior to first dose of study treatment.
- 3.2.4 Use of other investigational drugs within 28 days (or five half-lives, whichever is shorter; with a minimum of 14 days from the last dose) preceding the first dose of study drug(s) and during the study.
- 3.2.5 Patients with known brain metastases should be excluded from this clinical trial because of their poor prognosis and because they often develop progressive neurologic dysfunction that would confound the evaluation of neurologic and other adverse events.

Exception: Patients with brain metastases will be allowed on study if they have clinically controlled neurologic symptoms, defined as surgical excision and/or radiation therapy followed by 21 days of stable neurologic function and no evidence of CNS disease progression as determined by CT or MRI within 21 days prior to the first dose of study drug.

- 3.2.6 Have a known immediate or delayed hypersensitivity reaction or idiosyncrasy to drugs chemically related to trametinib, or excipients or to dimethyl sulfoxide (DMSO), or to compounds of similar chemical or biologic composition to navitoclax.
- 3.2.7 Current use of a prohibited medication. The following medications or non-drug therapies are prohibited:
 - Other anti-cancer therapy while on study treatment. (note: megestrol [Megace] if used as an appetite stimulant is allowed).
 - Concurrent treatment with bisphosphonates is permitted; however, treatment must be initiated prior to the first dose of study therapy. Prophylactic use of bisphosphonates in patients without bone disease is not permitted, except for the treatment of osteoporosis.
 - Because the composition, PK, and metabolism of many herbal supplements are unknown, the concurrent use of all herbal supplements is prohibited during the study (including, but not limited to, St. John's wort, kava, ephedra [ma huang], ginkgo

- biloba, dehydroepiandrosterone [DHEA], yohimbe, saw palmetto, or ginseng).
- Due to the expected dose-limiting toxicity of thrombocytopenia, the following concomitant medications are not allowed during navitoclax administration: Warfarin, clopidogrel (Plavix), ibuprofen, tirofiban (Aggrastat), and other anticoagulants, drugs, or herbal supplements that affect platelet function are excluded, with the exception of low-dose anticoagulation medications (such as heparin) that are used to maintain the patency of a central intravenous catheter. Aspirin will not be allowed within 7 days prior to the first dose of navitoclax or during navitoclax administration. However, subjects who have previously received aspirin therapy for thrombosis prevention may resume a low dose (*i.e.*, maximum 100 mg QD) of aspirin if platelet counts are stable (≥50,000/mm³) through 6 weeks of navitoclax administration. All decisions regarding treatment with aspirin therapy will be determined by the investigator in conjunction with the medical monitor.
- 3.2.8 Preclinical studies indicate that navitoclax is metabolized by CYP3A4, is a moderate inhibitor of CYP2C8, and is a strong inhibitor of CYP2C9. Therefore, caution should be exercised when dosing navitoclax concurrently with CYP2C8 and CYP2C9 substrates. Common CYP2C8 substrates include paclitaxel, statins, and glitazones, whereas CYP2C9 substrates include phenytoin and warfarin. When possible, investigators should switch to alternative medications or monitor the patients closely (particularly in the case of medications that have a narrow therapeutic window such as warfarin. Use of warfarin is specifically prohibited while on study). CYP3A inhibitors such as ketoconazole and clarithromycin are not allowed 7 days prior to the first dose of navitoclax or during navitoclax administration.

Because the lists of these agents are constantly changing, it is important to regularly consult a frequently-updated list such as http://medicine.iupui.edu/clinpharm/ddis/table.aspx; medical reference texts such as the Physicians' Desk Reference may also provide this information. As part of the enrollment/informed consent procedures, the patient will be counseled on the risk of interactions with other agents, and what to do if new medications need to be prescribed or if the patient is considering a new over-the-counter medicine or herbal product.

Patient instructions and information of possible drug interactions, contained in Appendix D, will be given to all patients upon enrollment in this study.

- 3.2.9 History or current evidence/risk of retinal vein occlusion (RVO).
- 3.2.10 History or evidence of cardiovascular risk including any of the following:
 - LVEF<LLN.
 - A OT interval corrected for heart rate using the Bazett's formula OTcB >480 msec.
 - History or evidence of current clinically significant uncontrolled arrhythmias
 (exception: patients with controlled atrial fibrillation for >30 days prior to enrollment

- are eligible).
- History of acute coronary syndromes (including myocardial infarction and unstable angina), coronary angioplasty, or stenting within 6 months prior to randomization.
- History or evidence of current ≥ Class II congestive heart failure as defined by the New York Heart Association (NYHA) functional classification system
- Treatment-refractory hypertension defined as a blood pressure of systolic >140 mmHg and/or diastolic >90 mmHg which cannot be controlled by anti-hypertensive therapy.
- Known cardiac metastases.
- Patients with intra-cardiac defibrillators.
- 3.2.11 Known Hepatitis B Virus (HBV), or Hepatitis C Virus (HCV) infection (patients with chronic or cleared HBV and HCV infection are eligible). Patients with Human Immunodeficiency Virus (HIV) are not eligible if on anti-retroviral medications.
- 3.2.12 Uncontrolled intercurrent illness including, but not limited to, ongoing or active infection, symptomatic congestive heart failure, unstable angina pectoris, cardiac arrhythmia, or psychiatric illness/social situations that would limit compliance with study requirements.
- 3.2.13 Subject has an underlying condition predisposing them to bleeding or currently exhibits signs of clinically significant bleeding.
- 3.2.14 Subject has a recent history of non-chemotherapy-induced thrombocytopenic-associated bleeding within 1 year prior to the first dose of study drug.
- 3.2.15 Subject has a significant history of cardiovascular disease (*e.g.*, MI, thrombotic or thromboembolic event in the last 6 months).
- 3.2.16 Pregnant women or nursing mothers. Animal reproductive studies have not been conducted with trametinib or navitoclax. Therefore, the study drug must not be administered to pregnant women or nursing mothers.

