Pneumonitis: At the 2 mg monotherapy dose, 0% to 4% of the subjects in five studies had pneumonitis (Investigator's Brochure, 2013). Of the nine total subjects (including crossovers) experiencing pneumonitis AEs at this dose, three subjects had grade 1 or 2 pneumonitis and six subjects had grade 3 pneumonitis.

Embryofetal toxicity: Based on its mechanism of action, trametinib can cause fetal harm when administered to a pregnant woman. Trametinib was embryotoxic and abortifacient in rabbits at doses greater than or equal to those resulting in exposures approximately 0.3 times the human exposure at the recommended clinical dose. If this drug is used during pregnancy, or if the patient becomes pregnant while taking this drug, the patient should be apprised of the potential hazard to a fetus.

Incidence of common AEs reported from a phase III trial of trametinib vs. chemotherapy in patients with advanced melanoma:

Patients with abnormal LVEF, history of acute coronary syndrome within 6 months, or current evidence of Class II or greater congestive heart failure (New York Heart Association) were excluded from this trial. Selected adverse reactions (AR) occurring in patients receiving trametinib as compared to patients in the chemotherapy arm are listed as below:

Table: Selected adverse reactions (ARs) occurring in $\geq 10\%$ of patients receiving trametinib AND at a higher incidence than in the chemotherapy arm (high in the trametinib arm compared with chemotherapy by $\geq 5\%$ in overall incidence or by $\geq 2\%$ grade 3 or 4 AEs)

		etinib 211)	Chemotherapy (n=99)		
Adverse Reactions	All Grades	Grades 3 and 4	All Grades	Grades 3 and 4	
Skin and subcutaneous tissue disorders					
Rash	57	8	10	0	
Dermatitis acneiform	19	<1	1	0	
Dry skin	11	0	0	0	
Pruritis	10	2	1	0	

Version Date: July 22, 2022

Paronychia	10	0	1	0
Gastrointestinal disorders				
Diarrhea	43	0	16	2
Stomatitis	15	2	2	0
Abdominal pain	13	1	5	1
Vascular disorders				
Lymphedema	32	1	4	0
Hypertension	15	12	7	3
Hemorrhage	13	<1	0	0

Table: Percent-patient incidence of laboratory abnormalities occurring at a higher incidence in patients treated with trametinib versus chemotherapy (between-arm difference of $\geq 5\%$ [all grades] or $\geq 2\%$ [grades 3 or 4])

		etinib 211)	Chemotherapy (n=99)	
Preferred term	All Grades	Grades 3 and 4	All Grades	Grades 3 and 4
Increased aspartate aminotransferase (AST)	60	2	16	1
Increased alanine aminotransferase (ALT)	39	3	20	3

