Macroscopic and microscopic changes indicative of lymphoid depletion occurred in lymphoid tissues at ≥ 30 mg/kg/day in rats and at ≥ 3 mg/kg/day in dogs, and were consistent with reductions in circulating lymphocytes (Investigator's Brochure, 2011). Affected lymphoid organs included lymph nodes and spleen (rats and dogs), thymus (rats only), and Peyer's patch (dogs only). Partial to complete reversibility of all effects on lymphoid tissue was noted.

Navitoclax had no clear adverse CNS effects in the rat and mouse at an intraperitoneally (IP) injected dose of 5 mg/kg (Investigator's Brochure, 2011). At doses of 10 mg/kg IP and higher, mild to moderate sedation occurred and latency to sleep increased after barbital injection. At doses of 25 mg/kg IP and higher, body temperature decreased as sedation became more pronounced. At 100 mg/kg IP, loss of traction was observed. Navitoclax produced no relevant effects on neurobehavioral function through the highest dose of 15 mg/kg (plasma concentrations of $137.9 \pm 27.5 \,\mu\text{g/mL}$).

Navitoclax does not pose a genotoxic risk, as it was negative in all genetic toxicity studies, and no effect on embryo-fetal development in rats or rabbits was observed (Investigator's Brochure, 2011).

In the Segment I male rat fertility study, navitoclax -related changes were limited to small and/or soft testes, decreased testis and epididymis weights, hypospermatogenesis, and reduced sperm motility and sperm counts at 30 mg/kg/day (top dose) following approximately 70 days of once daily oral dosing (Investigator's Brochure, 2011). In addition, time- and dose-dependent navitoclax -related effects were observed on the rat ovary. Ovarian atrophy (associated with \sim 58% decreased ovarian weights) was observed at the highest dose of 100 mg/kg in the 6-month study, characterized by reduction or absence or corpora lutea and reduction in number of developing follicles. Decreases in ovarian weights (up to \sim 29%) were observed at the lower doses in the 6-month study and in the shorter duration studies of 2 and 13 weeks in duration. These weight changes were

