considered not to be adverse due to the absence of associated histopathologic findings. However, no effect on reproductive performance was observed in male or female rats. No impairment of fertility was observed in the female rat Segment I study at up to 100 mg/kg/day (high dose). In Segment II embryo-fetal development studies, once daily oral doses of navitoclax in time-mated female rats (high dose, 100 mg/kg/day) and rabbits (high dose, 200 mg/kg/day) were not teratogenic and did not have any effect on the embryo/fetal viability of offspring.

Clinical Safety Profile

Navitoclax is being investigated as a single agent and as a component of combination therapy. Trial M10-454, a biocomparison study, is fully enrolled. Additionally, three phase 1/2a studies have completed and published safety and tolerability data from the phase 1 dose-escalation portions of the studies, and have transitioned to the phase 2a portions of the study:

- M06-814, in patients with relapsed or refractory lymphoid malignancies (Wilson *et al.*, 2010).
- M06-822, in patients with small-cell lung cancer (SCLC), pulmonary carcinoid, and other solid tumors (phase 1), and in patients with SCLC (phase 2a) (Gandhi *et al.*, 2011; Rudin *et al.*, 2012).
- M06-873, in patients with relapsed or refractory chronic lymphocytic leukemia (CLL) (Roberts *et al.*, 2012).

Thrombocytopenia has been the primary dose-limiting toxicity (DLT) in the clinical development of navitoclax. This has been observed nonclinically and is thought to be due to the pharmacodynamic effect of drug action (inhibition of the platelet-expressed homolog Bcl-X_L, leading to apoptosis) (Investigator's Brochure, 2011). Grade 3/4 thrombocytopenia was observed in 29 out of 55 patients in trial M06-814 (Wilson *et al.*, 2010); 5 out of 47 patients in the phase 1 portion of trial M06-822 and 16 out of 39 SCLC patients in the phase 2a portion (Gandhi *et al.*, 2011; Rudin *et al.*, 2012); and 8 out of 29 patients in trial M06-873 (Roberts *et al.*, 2012). Grade 4 thrombocytopenia and neutropenia were reversible via temporary suspension or dose reduction of navitoclax, and filgrastim for persistent grade 4 thrombocytopenia.

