- 3.1.9 All prior treatment-related toxicities must be CTCAE v4 grade ≤1 (except alopecia) at the time of enrollment. This requirement to return to ≤ grade 1 does not apply to immune checkpoint inhibitor related endocrinopathies (e.g. thyroiditis, hypophysitis, etc.) that necessitate hormone replacement therapy including, but not limited to levothyroxine, cortisol, and testosterone. CTCAE v5.0 will be utilized beginning April 1, 2018.
- 3.1.10 Patients must have normal organ and marrow function as defined below:
 - Leukocytes $\geq 3,000$ /mcL
 - Absolute neutrophil count (ANC) ≥1,200/mcL (subjects may be treated with hematopoietic growth factors to achieve or maintain this level)
 - Hemoglobin ≥9 g/dL
 - Platelets $\geq 100 \times 10^9 / L$
 - Albumin >2.5 g/dL
 - Total bilirubin ≤1.5x institutional ULN (patients with Gilbert's syndrome may have serum bilirubin >1.5×ULN)
 - Aspartate aminotransferase (AST) and alanine aminotransferase (ALT) ≤2.5x institutional ULN

- Serum creatinine ≤1.5 mg/dL *OR* calculated creatinine clearance (Cockroft-Gault formula) ≥50 mL/min *OR* 24-hour urine creatinine clearance ≥50 mL/min
- Prothrombin time (PT)/International normalized ratio (INR) and partial thromboplastin time (PTT) \leq 1.2x institutional ULN
- Left ventricular ejection fraction ≥ institutional lower limit of normal (LLN) by ECHO or MUGA
- 3.1.11 The effects of trametinib and navitoclax on the developing human fetus are unknown. For this reason, women of child-bearing potential and men with a female partner of child bearing potential must agree to use adequate contraception using *one of the methods listed below* prior to study entry, for the duration of study participation, and up to 4 months following completion of therapy.
 - total abstinence from sexual intercourse (minimum one complete menstrual cycle prior to study drug administration);
 - Vasectomized male subject or vasectomized partner of female subjects;
 - Hormonal contraceptives (oral, parenteral, transdermal or vaginal ring) for at least 3 months prior to study drug administration; if the subject is currently using a hormonal contraceptive, she should also use a barrier method during this study and for 1 month after study completion;
 - intrauterine device (IUD);
 - double-barrier method: male condom plus diaphragm or vaginal cap with spermicide (contraceptive sponge, jellies or creams);

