Men with a female partner of childbearing potential must have either had a prior vasectomy or agree to use effective contraception. Additionally, male subjects (including those who are vasectomized) whose partners are pregnant or might be pregnant must agree to use condoms for the duration of the study and for 4 months following completion of therapy.

Women of childbearing potential must have a negative serum pregnancy test within 7 days prior to initiation of treatment. Women will be considered not of childbearing potential if they are surgically sterile (bilateral oophorectomy or hysterectomy) and/or post-menopausal (amenorrheic for at least 12 months).

Should a woman become pregnant or suspect she is pregnant while she or her partner is participating in this study, she should inform her treating physician immediately. The potential hazard to the fetus should be explained to the patient and partner (as applicable).

3.1.12 Ability to understand and the willingness to sign a written informed consent document.

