Route(s) **of Administration:** Oral.

Method of Administration: Take navitoclax tablets with food.

Potential Drug Interactions:

CYP-mediated DDI: Navitoclax metabolizes via CYP3A4. Concomitant use of strong and moderate CYP3A4 inhibitors/inducers should be taken with caution. Use alternative medications if possible.

In vitro studies, navitoclax is a moderate inhibitor of CYP2C8, a strong inhibitor of CYP2C9 and a weak inhibitor of CYP2C19, CYP2D6 and CYP3A4 following a 300 mg QD dose. Use caution when navitoclax is administered with sensitive substrates of CYP2C8 and CYP2C9.

Navitoclax is not an inducer of CYP1A2, CYP2B6, CYP2C9 and CYP3A4 and therefore is not expected to have any potential for DDI via CYP. As for M13, it did not increase CYP1A2, CYP2B6 and CYP3A4 mRNA expression when tested at concentrations up to 30 μM.

Transporter mediated DDI: Navitoclax and M13 (navitoclax metabolite) are inhibitors of OATP1B1/3, with IC₅₀ values of 2.0 μ M (navitoclax) and 20.8 μ M (M13) but do not result in DDI based on the static model (OATP1B1/1B3, R<1.1). Navitoclax may inhibit P-gp and BCRP at therapeutic doses (I_{gut}/IC₅₀>10). Both navitoclax and M13 are P-gp and BCRP substrates but are not OATP1B1/3 substrates.

Navitoclax and M13 are not inhibitors of OCT1, OCT2, OAT1, OAT3, MATE1 or MATE2K. M13 is not an inhibitor of P-gp, BCRP, or BSEP in vesicles or in MDCK cells.

Plasma Protein Binding: Navitoclax was highly bound to plasma proteins across species. Protein binding was highest in the human and dog (99.99%) followed by the mouse, rat, and monkey (99.98%). For each species studied, the extent of binding was constant over the entire drug concentration range (10 to 500 μ g/mL) and the

binding was independent of gender. The results indicate that navitoclax will be highly bound (99.99%)

to proteins in human plasma at concentrations expected after a therapeutic dosage (Cmax of 6.5 $\mu g/mL$).

Patient Care Implications:

Women of child-bearing potential (WOCBP) and men must agree to use adequate contraception (hormonal or barrier method of birth control; abstinence) while on treatment with navitoclax (ABT-263) and at up to 30 days after the last dose of navitoclax (ABT-263). Male study subjects who are sexually active with a WOCBP (woman of child-bearing potential), even if the male subject has undergone a successful vasectomy, must agree to use condoms while on treatment and through at least 90 days after the last dose of study drug.

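### Section 3.2.16 says no animal reproductive studies exist although Section 2.2 reports them for both drugs, and 3.1.11 and 8.1.2 disagree on condoms after vasectomy

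*Combined protocol and SAP*

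**What the plan says.** **Animal data.** Section 3.2.16 excludes pregnant women and nursing mothers on the ground that "Animal reproductive studies have not been conducted with trametinib or navitoclax". Section 2.2.1.3 says "Trametinib was embryotoxic and abortifacient in rabbits", at exposures from about 0.3 times that in humans. For navitoclax, the nonclinical toxicology text in 2.2.2 describes a male fertility study ("In the Segment I male rat fertility study, navitoclax -related changes were limited to small and/or soft testes", together with lower organ weights and sperm changes), a female rat fertility study, and embryo-fetal work that begins "In Segment II embryo-fetal development studies, once daily oral doses of navitoclax in time-mated female rats" and extends to rabbits. Its summary is that "no effect on embryo-fetal development in rats or rabbits was observed".

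**Contraception.** Section 3.1.11 requires one method from a list, "prior to study entry, for the duration of study participation, and up to 4 months following completion of therapy". Vasectomy is on that list, and the text for men repeats it: "Men with a female partner of childbearing potential must have either had a prior vasectomy or agree to use effective contraception". Condoms become obligatory for vasectomized men only when the partner is pregnant or may be. Users of hormonal contraception are asked to add a barrier method during the study and for 1 month after it.

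Section 8.1.2, under the patient care text for navitoclax, accepts a hormonal or a barrier method, or abstinence, up to 30 days after the last navitoclax dose. It then sets a separate rule for sexually active men whose partners can conceive: "even if the male subject has undergone a successful vasectomy, must agree to use condoms while on treatment and through at least 90 days", counted from the final dose.

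**The concern.** A protocol should not deny in its exclusion criteria what it reports in its background. Anyone who reads 3.2.16 without turning back to Section 2.2 learns that there are no animal reproductive data, when one of the two drugs has a positive finding at less than human exposure.

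The contraception texts matter because both are worded as commitments that the patient has to give, and the protocol does not say which prevails. Registration (Section 4.2) works from a checklist of the inclusion and exclusion criteria. A vasectomized man can therefore be enrolled correctly under 3.1.11 without ever being asked for the condom commitment in 8.1.2. At stake are consistent protection of partners and a possible fetus, and avoidable deviations at sites. The efficacy and toxicity inferences are not at stake.

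**Working it through.** No sample size, power or error rate is involved, and the plan gives no figure to reproduce. The check is to set the sections side by side.

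**Step 1: is the statement in 3.2.16 true within the document?**

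- Trametinib (2.2.1.3): rabbit embryo-fetal toxicity is reported. An animal reproductive study was therefore done, and it was positive.
- Navitoclax, fertility (2.2.2, Segment I): studies in male and female rats. Males showed testicular and sperm changes. Female fertility was not impaired, and reproductive performance was unaffected in either sex.
- Navitoclax, embryo-fetal (2.2.2, Segment II): studies in rats and rabbits, with no teratogenicity and no effect on viability.
- Navitoclax, ovary (2.2.2): atrophy at the top dose came from the 6-month study. Lower ovarian weights at lower doses and in the 2- and 13-week studies were judged not adverse. These are repeat-dose findings, separate from the Segment I and II studies.

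The sentence is contradicted for both drugs. A negative study contradicts it as much as a positive one.

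**Step 2: do 3.1.11 and 8.1.2 agree?**

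| Item | 3.1.11 | 8.1.2 | Does meeting 3.1.11 meet 8.1.2? | Does meeting 8.1.2 meet 3.1.11? |
|---|---|---|---|---|
| Vasectomized man, partner able to conceive and not thought pregnant | Vasectomy is enough | Condoms as well, on treatment and 90 days or more after | No | Yes, on method |
| Post-treatment period | 4 months from completion of therapy | 30 days from last navitoclax dose | Yes | No |
| Hormonal user | Hormonal plus barrier | Hormonal or barrier | Yes | No |

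On duration, the shortest run of four calendar months is February to May: 28 + 31 + 30 + 31 = 120 days. That exceeds 30 days by 120 − 30 = 90 days. It also exceeds the 90-day condom minimum, so condom use for 4 months would satisfy that minimum. I read each stated limit as the period required.

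**Step 3: when does the period start?** Four starting points are in use. In 3.1.11 they are completion of therapy (the 4 months) and completion of the study (the added barrier). In 8.1.2 they are the last navitoclax dose (the 30 days) and the last dose of study drug (the 90 days). Section 6 opens by saying that when one drug is interrupted or discontinued, the other should continue. The 30-day period in 8.1.2 could therefore end while the patient still takes trametinib, and 8.1.1 contains no contraception text for that drug.

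**The case against.** The best defence is that 3.1.11 is the study-level criterion for the combination and 8.1.2 is background on one agent, so 3.1.11 governs. For duration and hormonal methods this largely stands: a patient who meets 3.1.11 meets 8.1.2, and the texts need harmonizing rather than choosing between. It does not dispose of the vasectomy point, where 3.1.11 asks for less than 8.1.2, and the protocol states no order of precedence. One might answer that any partner able to conceive might be pregnant, which would bring condoms back under 3.1.11. On that reading, however, the sentence in 3.1.11 accepting vasectomy would have no effect.

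A reader might infer more than the documents support:

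- **That the vasectomy rules are opposites.** They are not. Section 3.1.11 does not bar condoms and in one situation demands them. Section 8.1.2 is wider in scope, and both can be met together.
- **That a patient can be eligible under one section and ineligible under the other.** Section 4.2 ties eligibility to the inclusion and exclusion criteria. The wording of 8.1.2 invites doubt but does not make it a second entry test.
- **That both drugs were embryotoxic.** Only trametinib was; the navitoclax embryo-fetal studies were negative.
- **That patients are being miscounselled.** The consent pages are not available. Sections 2.2.1.3 and 3.1.11 both call for the fetal hazard to be explained, and 7.3.4.1 treats the agents as possibly teratogenic.
- **That 3.1.11 contradicts itself with 1 month against 4 months.** The 1 month limits the added barrier and runs from a different event.
- **That calling the effects unknown in 3.1.11 is false.** That sentence concerns the human fetus, and rabbit data do not strictly refute it.

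**Conclusion.** The point holds in two parts, with a secondary one.

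- The factual statement in 3.2.16 is wrong for both drugs on the protocol's own evidence. The exclusion it supports is sound and not questioned.
- Sections 3.1.11 and 8.1.2 disagree on condoms for vasectomized men whose partner can conceive but is not thought to be pregnant. Following 3.1.11 alone leaves 8.1.2 unmet for the whole of treatment and the 90 days or more after it.
- Secondarily, the post-treatment periods differ by about 3 months and the wording on hormonal methods differs. In both, following 8.1.2 alone falls short of 3.1.11.

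So neither section suffices alone. The conclusion rests on a plain reading of the current text and on the absence of any precedence statement. How many enrolled men are affected cannot be judged from the documents. Sample size, error rates and planned analyses do not change. I express no view on which contraception rule is right.

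**What to change.** - In 3.2.16, replace the sentence about animal studies with one consistent with 2.2.1.3 and 2.2.2, keeping the trametinib and navitoclax findings distinct. The exclusion stays as it is.
- Reconcile 3.1.11 and 8.1.2 in a single contraception rule stating who is covered, which methods count, how vasectomy is treated, how long the rule lasts, and from which event the time runs when the two drugs stop on different dates. The other section should refer to it. The sponsor and medical monitor decide the content.
- Check the consent form and the eligibility checklist against the reconciled text. While amending, consider whether the wording on unknown effects in 3.1.11 should point to 2.2.1.3; this is optional.

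The cost is a wording amendment and a consent check, with no change to design, sample size or analysis.
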